To the best of our knowledge, this is the first study to investigate the utility of a methylprednisolone taper six weeks to three months postoperatively following TKA. The authors present a double-blinded, randomized-controlled trial evaluating the role of a methylprednisolone taper on patients with decreased ROM or delayed recovery in the acute postoperative period.

VI. Study Design:

Level I: Prospective, double-blinded, randomized controlled trial

VII. Inclusion Criteria:

- Any patient undergoing primary TKA with a diagnosis of osteoarthritis
- \geq 18 years old
- ROM <90° by 3 weeks postoperatively without improvement to >90° by 6 weeks
- Requiring a 30-pill oxycodone refill
- NSAID allergy
- Thigh circumference discrepancy >2cm between legs from 3 to 6 weeks
- Defense and Veterans Pain Rating Scale (DVPRS) > 5 between 3 and 6 weeks
- Willingness to undergo randomization

VIII. Exclusion Criteria:

- Reported chronic corticosteroid or opiate use
- Suspected or confirmed periprosthetic joint infection
- Revision TKA
- Primary diagnosis other than osteoarthritis, including avascular necrosis, fracture, or post-traumatic arthritis
- American Society of Anesthesiologists (ASA) score ≥ 4
- Reported history of liver or renal disease
- Uncontrolled diabetes

- Immunosuppression
- \leq 18 years old
- Inability to take oral medications
- Unable to provide consent

IX. Demographics:

Age, sex, height, weight, BMI, ASA score, comorbidities, and smoking status will be collected

X: Primary Outcome Measure:

Change in ROM from pre-treatment to 8 and 12 weeks post-operatively

XI: Secondary Outcome Measures:

- 1. Patient Reported Outcome Measures:
 - a. DVPRS and Knee Society Score (KSS) at pre-treatment, and 1 week, 3 weeks, 6 weeks, 12 weeks post-treatment
 - b. Daily Visual Analogue Scale (VAS) pain score on days 1-6 of treatment
 - c. Knee Injury and Osteoarthritis Outcome Score for Joint Replacement (KOOS Jr), Veterans Rand 12-Item Health Survey (VR-12), Single Assessment Numeric Evaluation (SANE), Forgotten Joint Score, and UCLA activity score preoperatively, 6 weeks, and 3 months
- 2. Number of manipulations under anesthesia (MUAs)
- 3. Adverse outcomes including infection, avascular necrosis, and 90-day readmission rates

XII. Patients and Protocols:

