Patients will be enrolled in STREAMD, a text messaging service that texts prompts to patients. Daily text messages will include reminders with the required number of pills to be taken on the corresponding day of the taper. At the time of consent, knee flexion ROM will be recorded by the attending physician and this information will be extracted from the chart. ROM will then be extracted from patient charts weekly for eight weeks using clinic or physical therapy notes as needed. PROMs collected at the time of consent will include DVPRS and KSS. DVPRS and KSS will also be collected at one week, 3 weeks, 6 weeks, and 12 weeks post-treatment. DVPRS will be administered via STREAMD. Patients will respond directly via text message reply indicating a score. VAS pain score will be collected daily on days 1-6 of the taper, via STREAMD. KSS will be completed via the PatientIQ system, which is currently used for all research related forms. For any patient that cannot use these services, surveys will be administered over the phone. All patients, whether enrolled in studies or not, complete KOOS Jr, VR-12, SANE, Forgotten Joint, and UCLA scores preoperatively, and at six weeks and three months postoperatively.

XIII. Sample Size:

Power analysis used mean flexion of $111.4^{\circ} \pm 16.0^{\circ}$, reported by Bettger et al. at 6 weeks post-TKA.²⁸ Control and treatment groups are assumed to have the same standard deviation. Following precedent, a change in ROM of 10° was defined as clinically important.^{29, 30} At an alpha of 0.05, 112 patients (56 per arm) will provide 90% power to detect a 10° change. Assuming a 20% dropout, 136 patients (68 per arm) will be recruited.

XIV. Treatment Groups:

- 1. Methylprednisolone taper 21 x 4mg tablets at 6 weeks, qualifying for MUA if ROM <90° at 8 weeks
- 2. Placebo taper 21 sugar tablets at 6 weeks with standard management, qualifying for MUA if ROM <90° at 8 weeks

XV. Risks and Benefits:

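### Section XIII powers a change-from-pre-treatment outcome with a single-visit SD and no named primary model, so the 90% is conditional; name a model adjusted for flexion at consent and state power under it

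*Combined protocol and SAP*

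**What the plan says.** Section X defines the primary outcome as "Change in ROM from pre-treatment to 8 and 12 weeks post-operatively".

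Section XIII takes its only variance input from a cited trial: mean flexion 111.4° with SD 16.0° at 6 weeks after surgery. That is the spread of a level at one visit. It adds "Control and treatment groups are assumed to have the same standard deviation", treats 10° as clinically important, and concludes "At an alpha of 0.05, 112 patients (56 per arm) will provide 90% power to detect a 10° change". It then says "Assuming a 20% dropout, 136 patients (68 per arm) will be recruited".

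Section XII provides a pre-treatment value: "At the time of consent, knee flexion ROM will be recorded by the attending physician". The same section makes the day of consent the first day of treatment.

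The combined document has no statistical analysis section. It gives no primary test, model, covariate, SD of change or pre/post correlation, and it does not say whether alpha is one- or two-sided.

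**The concern.** The spread of a change is not the spread of a level. It depends on the SD at each visit and on the correlation r between them. The one equal-SD assumption in the plan compares the arms, so it says nothing about how the spread at consent relates to the spread at follow-up. A reader cannot tell whether 90% describes the analysis that will be run.

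Two things are at stake. The first is whether the power statement can be checked. The second is precision: an unadjusted change, a baseline-adjusted model and a plain follow-up comparison all remain open, and they can differ in power. Validity is not at stake, because an unadjusted comparison of change is unbiased under randomization.

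**Working it through.** **Inputs from the plan.** Difference 10°, SD 16.0°, alpha 0.05, 56 per arm, 136 recruited, 20% dropout (Section XIII). ROM is read as knee flexion, as recorded in Section XII.

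**Reviewer assumptions, because the plan gives none of these.** Two-sided test; the 10° is the difference between arms; one time point; follow-up SD sf = 16°; pre-treatment SD sb = 16°, 12° or 8°; r varied. All powers use the noncentral t distribution.

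**1. The plan's figure.** Noncentrality = 10 / (16 × √(2/56)) = 3.31 with 110 df. Power is 90.6%, so the stated 90% is reproduced as a single-visit comparison.

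**2. Number left after dropout.** 136 × 0.8 / 2 = 54.4, or about 54 per arm. The same single-visit comparison then has 89.6% power. Keeping 112 after 20% dropout would need 112 / 0.8 = 140.

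**3. Unadjusted change.** Variance of change = sf² + sb² − 2·r·sf·sb. At r = 0.3:

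| sb | Variance of change | SD of change | Power, 56 per arm | Power, 54 per arm |
|---|---|---|---|---|
| 16° | 256 + 256 − 153.6 = 358.4 | 18.93° | 79.1% | 77.6% |
| 12° | 256 + 144 − 115.2 = 284.8 | 16.88° | 87.5% | 86.2% |
| 8° | 256 + 64 − 76.8 = 243.2 | 15.59° | 92.0% | 91.0% |

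At r = 0.5 with 56 per arm, power is 90.6%, 95.3% and 96.6% for sb = 16°, 12° and 8°. The largest SD that still gives 90% with 56 per arm is 16.18°. The break-even correlation is r = (256 + sb² − 16.18²) / (32·sb), which is about 0.49, 0.36 and 0.23.

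**4. Adjusted for flexion at consent.** Residual variance = sf²(1 − r²). The variance of change can be written as sf²(1 − r²) + (sb − r·sf)². The second term is a square, so the adjusted residual variance is never the larger, whatever r and sb are. Power uses 2n − 3 df, without and then with the factor 1 + 1/(2n − 4) for chance baseline imbalance:

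| r | Residual SD | 56 per arm | 54 per arm |
|---|---|---|---|
| 0 | 16.00° | 90.6% / 90.4% | 89.6% / 89.3% |
| 0.3 | 15.26° | 93.0% / 92.8% | 92.1% / 91.9% |

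The pre-treatment SD no longer enters. The finite-sample cost of estimating the covariate effect is at most about 0.4 percentage points. Simulation with SD 16° at both visits and r = 0.3 agrees: 92.8% adjusted against 79.1% for unadjusted change with 56 per arm.

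**The case against.** The strongest reply is that no error is shown. The stated 90% reproduces, an unadjusted change is a legitimate analysis, and every figure below 90% with 56 per arm needs an r and a pre-treatment SD that the plan does not give. One inclusion criterion is "ROM <90° by 3 weeks postoperatively without improvement to >90° by 6 weeks". If it applied to every patient, the pre-treatment SD would probably be narrower than 16°, and the gain from adjustment would shrink: at r = 0.3, from about 14 points (79.1% to 93.0%) to about 1 point (92.0% to 93.0%) at 8°. At r = 0.5 there would be no shortfall with 56 per arm under any of the three SDs.

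All of that stands. A reader might infer from the 79% that the trial is underpowered. The documents do not support that reading, because they fix neither r nor the pre-treatment SD, and the inclusion list does not make clear whether the <90° criterion applies to everyone. What the reply leaves untouched is that the plan names no model and gives no basis for carrying a single-visit SD over to a change.

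Three further limits also stand:
- A follow-up SD other than 16° could go either way, so an upward-only sensitivity range would be one-sided. At r = 0.3 and 56 per arm, an SD of 14° gives about 97%.
- The plan states no rule for splitting alpha between 8 and 12 weeks, and Section IV points to two weeks after treatment starts, so power under a split would be speculation.
- The figures are for one time point. They do not describe a repeated-measures model. They also do not allow for manipulation under anesthesia, for which patients can qualify at 8 weeks, before the 12-week measurement.

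**Conclusion.** The point holds as a gap in specification and precision. The 90% is correct for a two-sided, single-visit comparison with SD 16° and 56 per arm. For an unadjusted change it is conditional: with follow-up SD 16° and r = 0.3, power runs from 79% to 92% as the assumed pre-treatment SD falls from 16° to 8°.

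Adjusting for flexion at consent removes the dependence on the pre-treatment SD. Apart from the small finite-sample cost, it is never less precise than the unadjusted change. A reader might take it to guarantee 90%. It does not: the result still depends on the follow-up SD, the number analysed and how the two time points are used. With 54 per arm and r = 0, it is already about 89-90%. The point should be addressed, but it does not threaten the trial's validity.

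**What to change.** (a) Name the primary analysis: a linear model of follow-up flexion (or, equivalently, of change) on treatment arm and the flexion recorded at consent. State how the 8- and 12-week time points are used.

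(b) In Section XIII, state that 16° is the assumed within-arm SD of follow-up flexion, that 10° is the difference between arms, and that power is for one time point at two-sided 0.05 under the adjusted model. Suitable figures are about 90-91% at r = 0 with 56 per arm and about 89-90% at r = 0 with the 54 per arm left after 20% dropout from 136, both higher for r above 0. If a sensitivity range for the SD is added, it should go in both directions and be justified by the sponsor. If a repeated-measures model is chosen instead, power should be worked out for that model.

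(c) Optionally, adjust the Defense and Veterans Pain Rating Scale (DVPRS) and Knee Society Score (KSS) for their consent values in the same way, since "PROMs collected at the time of consent will include DVPRS and KSS".

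The cost is one paragraph of analysis wording and a few sentences in Section XIII. No extra patients or data are needed.

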Appendix 1: Dosing Schedule

| | Before Breakfast | After Lunch | After Dinner | Before Bedtime |
|-------|------------------|-------------|--------------|----------------|
| Day 1 | 2 capsules | 1 capsule | 1 capsule | 2 capsules |
| Day 2 | 1 capsule | 1 capsule | 1 capsule | 2 capsules |
| Day 3 | 1 capsule | 1 capsule | 1 capsule | 1 capsule |
| Day 4 | 1 capsule | 1 capsule | X | 1 capsule |
| Day 5 | 1 capsule | X | X | 1 capsule |
| Day 6 | X | X | X | 1 capsule |
